APPENDIX 1: QUALITY OF LIFE QUESTIONNAIRE: SGRQ-I (25)

(Attachment)

APPENDIX 2: QUALITY OF LIFE QUESTIONNAIRE: L-IPF (26,27)

(Attachment)

APPENDIX 3: DYSPNEA QUESTIONNAIRE: mMRC (28,29)

The modified Medical Research Council dyspnea scale is a simple one question tool to evaluate the patient's current state of dyspnea. It will be provided via multiple formats (available electronically via a RED Cap survey invitation, available on the patientMpower app, and in paper form).

Please choose the one best response to describe your shortness of breath.

Grade

- 0 "I only get breathless with strenuous exercise."
- 1 "I get short of breath when hurrying on the level or walking up a slight hill."
- 2 "I walk slower than people of the same age on the level because of breathlessness or have to stop for breath when walking at my own pace on the level."
- 3 "I stop for breath after walking about 100 yards or after a few minutes on the level."
- 4 "I am too breathless to leave the house" or "I am breathless when dressing."

An increased score reflects impaired quality of life and a high symptom burden. In practice, this scale may be used to help identify increased need for palliative care. (29)

APPENDIX 4: DEPRESSION SELF-SCREEN TOOL

Grief & Depression

Everyone who is diagnosed with a serious lung disease, as well as their loved ones, will experience episodes of deep sadness & grief, and these feelings will usually wax & wane throughout the disease process.

It's important to reach out for help if these feelings become prolonged or otherwise start to interfere with your quality of life; asking for help is not a sign of weakness – it is a sign of strength that you are taking back some control over your own life and health. Take the Depression Self-Screen below to see how sadness & grief may be affecting you, then turn to the end of this booklet for a list of resources to help.

Depression Self-Screen*

	Not At All	Several Days	More Than Half the Days	Nearly Every Day
Over the last two weeks, how often have you been bothered by feeling little interest or pleasure in doing things?				
Over the last two weeks, how often have you been bothered by feeling down, depressed, or hopeless?				
Over the last two weeks, how often have you been bothered by having trouble falling or staying asleep, or sleeping too much?				
Over the last two weeks, how often have you been bothered by feeling tired or having little energy?				
Over the last two weeks, how often have you been bothered feeling bad about yourself – or that you are a failure or have let yourself or your family down?				
Over the last two weeks, how often have you had problems with moving or speaking so slowly that other people could have noticed?				
Over the last two weeks, how often have you had thoughts that you would be better off dead, or of hurting yourself?				
If you checked off any problems, how difficult have these problems made it for you at work, home, or with other people?	Not Difficult	Somewhat Difficult	Very Difficult	Extremely Difficult
Add	0 For each box checked	1 For each box checked	2 For each box checked	3 For each box checked

Total For Each Column				
Total of All Columns = Depression Score				

0 – 6: None to Mild Depression

7 – 15: Moderate Depression (*seeking outside help is recommended*)

16 – 24: Severe Depression (*it is critically important that you seek outside help as soon as possible*)

**Adapted from the Mental Health America Depression Screening Tool*

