5. To evaluate patient management at ILD Center compared to outlying community centers among the groups and as stratified by class.
6. To evaluate a standardized protocol that includes a structured educational curriculum followed by a regularly timed disease-focused phone calls with protocolized interventions when disease progression is recognized.

Study Design

This is a single-center prospective randomized study to compare outcomes on hospitalization, healthcare compliance, and quality of life of telenursing with or without remote monitoring as compared to usual care. All patients diagnosed with IPF at the Vanderbilt Medical Center outpatient Pulmonary Clinic, who meet inclusion and exclusion criteria, will be asked to participate. Patients who agree to participate and sign consent will be randomized into one of three treatment arms: usual care (the control group), usual care with telenursing, usual care with telenursing and remote monitoring. Patients will be asked to participate in the study for at least one year. We expect to enroll 150 patients, or 50 patients into each arm.

Usual care (Arm 1) – Patients will continue to receive education in the clinic and telephonically about their lung disease, medications, and oxygen use. At the point of diagnosis, patients will be given our current educational materials to take home and review, as well as our contact information. Patients will continue to attend face-to-face visits in the out-patient setting. The frequency of visits will be based on the discretion of the provider. During these visits, the patient will continue to receive individualized standard of care, which may include some or all of the following: a face-to-face visit with a healthcare provider, vital signs, with pulse oximetry at rest, weight measurement, pulmonary function testing, a six-minute walk, and laboratory testing. Other testing, such as echocardiography or chest radiography, may be required based on need. If patients do not return to Vanderbilt Medical Center beyond the point of diagnosis, they will still be allowed to participate. The usual care of local healthcare providers will be collected.

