In addition to usual care, patients will be asked to answer five questionnaires to provide information about quality of life, depression, anxiety, dyspnea, and compliance and disease-state knowledge. These questionnaires will be given at the point of diagnosis, at 3 months, then 6 months, and then at 6-month intervals until the patient dies or is transplanted. Patients will be given paper-based questionnaires if they do not have the ability to complete them on-line via the RED Cap portal. These questionnaires to be conducted are the St. George's Respiratory Questionnaire-IPF Specific (SGRQ-I), Living with IPF (L-IPF for symptoms and impact), the modified Medical Research Council dyspnea scale (mMRC), a Depression Self-Screen (adapted from the Mental Health America Depression and Anxiety Screening Tools), an Anxiety Self-Screen (adapted from the New Zealand Health Promotion Agency Anxiety Self-Test), and the IPF Treatment Compliance and Knowledge Questionnaire. These are located in Appendices 1-6.

Usual Care with Telenursing – Patients will continue to receive ‘usual care’ as outlined above (with the questionnaires), however, will also receive scheduled one-on-one teaching support telephone calls with a nurse or nurse practitioner who have clinical expertise in the treatment and management of idiopathic pulmonary fibrosis. Telenursing will consist of an 8-week “Educational Phase” followed by periodic phone calls during the “Management Phase”. During the Educational Phase telephone dialogue will be streamlined and remain on the topic of education, while only briefly discussing symptoms or side effects of medications as needed. During the Management Phase telephone dialogue will be focused on assessing symptoms of acute exacerbation or other respiratory concerns, adherence to treatments, including oxygen therapy and pulmonary rehabilitation, as well as follow up regarding known associated comorbidities. Re-education of previous modules will be provided as needed. The mMRC will be assessed with each phone call. Telenursing visits will be scheduled with the patient during an Introductory Phone visit from the nurse practitioner. Visits will be conducted telephonically or via a secure portal (ZOOM). An outline of Educational Phase topics as well as the plan for Management Phase telephone calls is provided in Appendix 7.

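### The depression form bands by total score alone, so near-daily thoughts of death or self-harm can score as None to Mild, and no step in the available text brings that answer to a clinician

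*Combined protocol and SAP*

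**What the plan says.** **The form.** Appendix 4 has seven symptom rows and one difficulty row, each scored 0 to 3. One symptom row asks "how often have you had thoughts that you would be better off dead, or of hurting yourself". The column totals are added to give the depression score, and the bands use only that sum. The lowest band reads "0 – 6: None to Mild Depression" and carries no advice. The middle band (7 to 15) recommends outside help. The top band (16 to 24) calls such help critically important. No rule attaches to any single item.

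**Advice to all respondents.** The introduction to Appendix 4 tells everyone to "reach out for help if these feelings become prolonged or otherwise start to interfere with your quality of life", to take the self-screen, and "then turn to the end of this booklet for a list of resources to help".

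**Schedule and mode.** Under Study Design, the questionnaires are "given at the point of diagnosis, at 3 months, then 6 months, and then at 6-month intervals". The arms with telenursing include the same questionnaires as usual care. On mode: "Patients will be given paper-based questionnaires if they do not have the ability to complete them on-line via the RED Cap portal". Data Collection lists questionnaire scores among the data captured and states no review step.

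**Contact with patients.** For Arm 1, Study Design says: "Patients will continue to receive education in the clinic and telephonically about their lung disease, medications, and oxygen use". Face-to-face outpatient visits also continue, at the provider's discretion. It adds: "If patients do not return to Vanderbilt Medical Center beyond the point of diagnosis, they will still be allowed to participate". For Arms 2 and 3, Appendix 7 makes comorbidity review a standing topic of the management calls. The Telenursing text provides for telling local clinicians the outcomes of those calls.

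**The concern.** Two separate things are at issue.

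1. **The scoring rule.** Because only the total is banded, the most serious answer on the form can sit under the most reassuring label. This happens when the rule is followed exactly. It does not depend on an error or an unusual reading.

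2. **Routing.** Whatever the total, the text does not say who reads the answer. The study itself asks this question in all three arms at baseline and at months 3, 6 and 12, and every six months after that. Its Background describes depression as a common and significant comorbidity of IPF. A study that collects this answer should state who looks at it and when.

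What is at stake is the safety of an individual participant. The ordinal composite of hospitalizations and death does not use this form.

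**Working it through.** **Inputs (all from Appendix 4 unless noted).** Eight rows, each 0 to 3; score = sum of all columns; bands 0–6, 7–15 and 16–24. Planned enrolment is 150, 50 per arm (Study Design). First-year forms fall at baseline and months 3, 6 and 12.

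**Step 1: reproduce the form's range.** 8 × 3 = 24, which matches the top of the highest band. The seven symptom rows alone give 7 × 3 = 21, which does not. So the difficulty row is counted.

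**Step 2: room left in the lowest band.** If the self-harm item scores s, the other seven rows may add up to 6 − s before the band changes:

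| Self-harm answer | s | Points allowed elsewhere | Totals still in the lowest band |
|---|---|---|---|
| Nearly every day | 3 | 6 − 3 = 3 | 3 to 6 |
| More than half the days | 2 | 6 − 2 = 4 | 2 to 6 |
| Several days | 1 | 6 − 1 = 5 | 1 to 6 |

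**Step 3: concrete answer sets with the item at 3.**
- Self-harm 3 + worst difficulty rating 3 + all else 0 = 6.
- Self-harm 3 + feeling down or hopeless 3 + no difficulty 0 = 6.
- Self-harm 3 + sleep trouble 1 + tiredness 1 + some difficulty 1 = 6.

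All three are classed None to Mild.

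**Step 4: full count of patterns.** The other seven rows have 4^7 = 16,384 answer patterns. Those that keep the total at 6 or below are:
- item at 3: C(10,7) = 120;
- item at 2: C(11,7) − 7 = 330 − 7 = 323;
- item at 1: C(12,7) − 7 × 8 = 792 − 56 = 736.

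The subtractions remove patterns in which one row would exceed 3. With the item at 3 this is 120 / 16,384 = 0.7% of patterns. For any positive answer it is (120 + 323 + 736) / (3 × 16,384) = 1,179 / 49,152 = 2.4%. These figures show only that the gap exists and is bounded. Patterns are not equally likely, so they are not probabilities.

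**Step 5: other readings of the difficulty row.** If a patient who checks any problem must rate difficulty at 1 or more, the lowest-band totals with the item at 3 narrow to 4–6 (36 patterns). If the row is left out of the sum, they remain 3–6. The result stands on either reading.

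**Step 6: trace the answer through the text.**

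| Contact or rule | Where | Tied to this item? |
|---|---|---|
| Advice to reach out; resource list | Appendix 4 introduction | No; general and self-directed |
| Questionnaire scores collected | Data Collection | No review step stated |
| Visits and telephone education, Arm 1 | Study Design | Not tied to the form |
| First-week follow-up call | Appendix 7 | Not tied to the form |
| Comorbidity review, Arms 2 and 3 | Appendix 7, Management Phase | Not tied to the form |
| Written Visit A and B scripts | Appendix 7 | No mood question |
| In-call escalation | Appendix 7, Respiratory Event | Respiratory event or progression only |
| Call outcomes sent to local clinicians | Study Design, Telenursing | Calls, not form answers |
| Saturation and FVC contact rules | Study Design, Arm 3 | No; patient-initiated, physiological |

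No row carries the self-harm answer from the form to a clinician, whether the total is 3 or 24.

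**Step 7: forms to be screened.** 150 × 4 = 600 in year 1. This is a maximum, because it assumes full enrolment and every form returned.

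**The case against.** The strongest reply is that a patient in the lowest band is not left without help. The introduction speaks to every respondent and has two limbs: feelings that are prolonged, or feelings that interfere with quality of life. Near-daily thoughts over two weeks arguably meet the first limb even when no difficulty is recorded. Arm 1 patients keep seeing providers face to face. Arms 2 and 3 have comorbidity review on management calls and are introduced to support groups. The phrase about known associated comorbidities may well mean those known to accompany IPF, which would include depression. The referral list on the sixth education call ends in a question mark and need not be closed. The label also reaches the patient only if the page is self-scored or REDCap displays the band, which the text does not state.

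All of this stands, and it rules out some stronger readings. A reader might infer that patients reporting self-harm thoughts get no advice, or that Arm 1 has no clinician contact after the first week. The documents support neither. What the reply does not supply is a link: none of these contacts is tied to the form or the item, the advice relies on the patient to act, and patients who do not come back to the centre may stay enrolled.

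A second reply is that a procedure may exist elsewhere. The opening pages, consent pages, call slide decks, Appendix 11 flowchart and booklet resource list were not available. This also stands. The routing point is confined to the available text, and nobody should infer that the centre has no procedure. Even so, a procedure elsewhere would not change the printed band.

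**Conclusion.** The concern holds and should be acted on, with medium confidence.

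- **Banding:** certain from Appendix 4. Near-daily thoughts of death or self-harm can total 3 to 6 and be classed None to Mild. Its effect on what the patient reads depends on the band being seen.
- **Routing:** no step in the available text brings this answer to a clinician, at any total and in any arm. This rests on the available text alone.

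The number of patients affected cannot be estimated. A reader might be tempted to use the 25% with depressive symptoms in the cohort cited in the Background, or to read the pattern counts as frequencies. Neither measures how often this item is answered positively, and the documents give no such rate.

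This is a patient-safety matter only. The primary endpoint and its analysis are not affected.

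**What to change.** 1. Add one line to the Appendix 4 bands: any positive answer to the self-harm item warrants seeking help, whatever the total.
2. Set a REDCap alert on that item, and check paper forms for it on receipt, in all three arms. The clinical team decides the alert threshold and the response.
3. If a centre procedure already covers this, cross-reference it in the protocol. The band wording should still be changed.

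**Cost.** One wording change, one alert and a check of incoming paper forms, plus some existing staff time to review flagged forms out of at most 600 in year 1. At an assumed flag rate of 1% to 10% (the documents give none), that is 600 × 0.01 = 6 to 600 × 0.10 = 60 reviews. Randomization, endpoints and analysis do not change.

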APPENDIX 5: ANXIETY SELF-SCREEN TOOL

Anxiety

Feelings of anxiety are very common with a diagnosis of serious disease, especially serious lung disease because our bodies naturally experience intense anxiety when we feel very short of breath or see a loved one experiencing severe shortness of breath. Patients and loved ones often experience periods of anxiety throughout the disease process, and these symptoms may occur separate from or together with feelings of grief or depression.

It's important to reach out for help with symptoms that are interfering with your quality of life; asking for help is not a sign of weakness – it is a sign of strength that you are taking back some control over your own life and health. Take the Anxiety Self-Test below to see how anxiety may be affecting you, then turn to the next page for a list of resources to help.

Anxiety Self-Test*

	Not At All	Several Days	More Than Half the Days	Nearly Every Day
Over the last two weeks, how often have you been bothered by feeling nervous, anxious or on edge?				
Over the last two weeks, how often have you been bothered by not being able to stop or control worrying?				
Over the last two weeks, how often have you been bothered by worrying too much about different things?				
Over the last two weeks, how often have you been bothered by having trouble relaxing?				
Over the last two weeks, how often have you been bothered by being so restless that it is hard to sit still?				
Over the last two weeks, how often have you been bothered by becoming easily annoyed or irritable?				
Over the last two weeks, how often have you been bothered by feeling afraid as if something awful might happen?				
Over the last two weeks, how often has worrying caused you physical symptoms, such as stomach upset, rapid breathing or heart rate, etc.?				
Add	0 For each box checked	1 For each box checked	2 For each box checked	3 For each box checked
Total For Each Column				
Total of All Columns = Anxiety Score				

0 – 8: None to Mild Anxiety

9 – 15: Moderate Anxiety

16 – 24: Severe Anxiety

**Adapted from the New Zealand Health Promotion Agency Anxiety Self-Test*

APPENDIX 6: TREATMENT COMPLIANCE QUESTIONNAIRE

The following questionnaire will be given to patients at Baseline, Month 3, Month 6, then every 6 months. This will be given as a survey via the RED Cap database, or as a paper-based product for the patient to complete and return. The purpose of this survey is to evaluate patient-reported compliance with IPF treatments and therapies, as well as evaluate the patient's general knowledge about his disease. Both sections of the questionnaire will be scored. The values of the answers for the Compliance Section are recorded in parenthesis below. The scoring of the Educational Section is as follows: Completely agree = 3 points, Mostly agree = 2 points, Somewhat agree = 1 points, Do not agree = 0 points. A higher score will reflect an overall greater compliance or knowledge level.

Compliance section

Do you take your IPF medication (nintedanib or pirfenidone) daily and as prescribed?

- A. Yes, I take my medication for IPF daily (3)
- B. Yes, I take my medication for IPF daily, but not always as prescribed. (3)
- C. No, I do not take my medication daily, but take it most days of the week. (2)
- D. No, I only take my medication less than half the days in a week. (1)
- E. No, I do not take my medication. (0)
- F. This is not applicable to me because I am not currently prescribed IPF medication. (n/a)

Do you get your safety labs completed for your IPF medication monthly or quarterly?

- A. Yes, I get my safety labs completed monthly. (3)
- B. Yes, I get my safety labs completed quarterly. (3)
- C. No, I get my safety labs completed less frequently than quarterly. (1)
- D. No, I do not get any lab work completed regularly for my IPF medication. (0)
- E. This is not applicable to me because I am currently not on prescribed IPF medication. (n/a)

Do you wear your oxygen as prescribed?

- A. Yes, I wear my oxygen as prescribed. (3)
- B. No, I wear my oxygen according to how I need it. (1)
- C. No, I do not wear my oxygen. (0)
- D. This question does not apply to me because I am currently not prescribed oxygen. (n/a)

Do you exercise most days a week?

- A. Yes, I exercise every day. (3)
- B. Yes, I exercise most days a week (at least 4 days a week). (2)
- C. No, I exercise less than 4 days a week. (1)
- D. I do not exercise. (0)

Do you take your medication to control reflux / GERD daily?

- A. Yes, I take my medication for reflux / GERD daily and as prescribed. (3)
- B. No, I do not take my medication for reflux / GERD daily, but take it most days of the week. (2)

- C. No, I only take my reflux / GERD medication less than half the days in a week. (1)
- D. No, I only take my reflux / GERD medication when I need it. (1)
- E. No, I do not take my reflux / GERD medication. (0)
- F. This is not applicable to me because I am currently not prescribed reflux / GERD medication. (n/a)

Do you wear your cpap or bipap mask every time you sleep?

- A. Yes, I wear my cpap or bipap every night. (3)
- B. No, I wear my cpap or bipap most days a week (at least 4 days a week). (2)
- C. No, I wear my cpap or bipap less than 4 days a week. (1)
- D. No, I do not wear my cpap or bipap. (0)
- E. This is not applicable to me because I do not have sleep apnea that requires treatment with cpap or bipap. (n/a)

Knowledge section

I understand my lung disease.

- A. Completely agree
- B. Mostly agree
- C. Somewhat agree
- D. Do not agree

I understand how my IPF medication has been shown to help me.

- A. Completely agree
- B. Mostly agree
- C. Somewhat agree
- D. Do not agree

I understand the side effects associated with my IPF medications.

- A. Completely agree
- B. Mostly agree
- C. Somewhat agree
- D. Do not agree

I understand the importance of regular exercise.

- A. Completely agree
- B. Mostly agree
- C. Somewhat agree
- D. Do not agree

I understand why I need (or may need) to wear oxygen.

- A. Completely agree
- B. Mostly agree

- C. Somewhat agree
- D. Do not agree

I know when to call my IPF healthcare provider.

- A. Completely agree
- B. Mostly agree
- C. Somewhat agree
- D. Do not agree

APPENDIX 7: TELENURSING OUTLINE AND SCRIPTS FOR EDUCATIONAL, MANAGEMENT, and RECOGNIZED RESPIRATORY EVENT TELEPHONE CALLS

Introductory Phone Call – with the nurse practitioner and within the first week of the initial visit

Purpose 1: IF NOT CONSENTED TO THE STUDY IN THE CLINIC – the NP will discuss this study with the patient during the usual care appointment follow-up phone call. If the patient verbally agrees, a consent will be sent to the patient for signature and randomization will occur.

Purpose 2: IF ASSIGNED TO TELENURSING OR TELENURSING WITH REMOTE MONITORING: the phone call will not only be the usual care appointment follow-up phone call, but will explain telenursing (and remote monitoring, as randomization requires), and set up Educational Phase phone call times, as well as introduce available support groups (local, internet). IF POSSIBLE: The Educational Phone Call # 1 may occur at this time.

Education Phase

Educational phone contact should be scheduled with the patient at his or her convenience and at weekly intervals. The goal is to complete all 8 phone calls within 3 months of enrolling. Please see the power point slide decks associated with each phone call for teaching and script.

Education Phone Call # 1 – review of disease state / procedures / team

Education Phone Call # 2 – IPF FDA-approved medication benefits / risks (or side effects)

Education Phone Call # 3 – tobacco cessation / pulmonary rehabilitation

Education Phone Call # 4 – symptoms management / Importance of wearing your oxygen / AEx

Education Phone Call # 5 – clinical trials

Education Phone Call # 6 – comorbidity management – refer to GI, Sleep, PH (echo)?

Education Phone Call # 7 – lung transplant team (if applicable)

Education Phone Call # 8 – integrative health / palliation / hospice

Management Phase

Management Phone Calls will occur within one week following known provider visits and at intervals between known provider visits to begin within one-week of the post-~3 month follow up visit to discuss outcomes of visit / unanswered or new questions / assurance of follow up. Management Phone Calls will continue until the patient dies or is transplanted. Please see the Management Call power point slide deck or the scripts written below regarding the below topics of discussion:

Med review (side effects, dosing, labs)

Office visits / hospitalization review

Comorbidity review

Assessment of symptoms of AEx IPF / pneumonia / bronchitis /mMRC

PR/Exercise routine?

Oxygen use?

PRN Reminders regarding vaccines

Respiratory Event

If during the process of an educational or management call, the nurses recognizes the symptoms of disease progression or respiratory event, the nurse will utilize the following intervention. Please see the power point slide deck for scripts regarding respiratory event and disease progression.

Associated Script for Telenursing Management Visits

Visit A – within one week of office appointment

Focus is on ensuring understanding of diagnosis, inform of test results, ensure all orders have been started/completed (medications, referrals, etc), follow-up established.

Greeting

Hello. I'm calling to follow up on your appointment with Dr. ____ / NP ____ this past week at Vanderbilt Medical Center. How are you doing?

General understanding from visit

I just want to follow up to ensure you understand everything about your visit at Vanderbilt. I see from your healthcare provider's note, you were in the office for a ____ visit. Do you have any questions or concerns about your visit?

Review Medical Note – symptom review

During your visit you informed your doctor about your ____ symptoms _____. During the visit, Dr. ____ stated you could do ____ to control these symptoms. How are your symptoms today?

Review Medical Note – procedures / test results

*test results only advised when approved on by the ordering physician.

During your office visit, Dr. ____ ordered some ____ blood tests / xrays / etc. These are / are not back yet. May I review them with you?

Review Medical Note – all follow up

During your office visit, Dr. ____ wanted you to _____. Have these been set up yet?

(referrals for pulmonary rehab, other doctors to evaluate other problems, other studies, medications).

Review of phone call and End of call

Ensure all items have been completed, or are in the works. Ensure understanding of visit / diagnosis. Remind that you will call prior to next appointment.

Visit B – At midpoint between scheduled office appointment

Focus is on health status – is the patient well, or improving, or declining. Also touching compliance regarding medication, oxygen use, and exercise.

Greeting

Hello. This is _____, the _____ at Vanderbilt. I'm calling to check in with you. How are you doing?

Compliance measures

You are taking _____ - are you remembering to take it as prescribed? Any trouble with side effects? How are you managing this? Your pharmacy is _____. Any problems with getting your medications?

Double check lab schedule – have they had labs / need labs?

You are wearing oxygen? Current liter flow is __ with rest and __ with exercise. Your current DME is _____. Any changes to this? Do you have enough oxygen for your needs both inside and outside of your home?

You are exercising? Pulmonary Rehabilitation or at home? How many days a week?

Do you have sleep apnea and need PAP therapy? Are you wearing your mask? Any problems with this? Your DME is _____.

IPF Symptom Control – stable, worsening?

How is your shortness of breath? What makes you short of breath?

How is your cough?

How is your fatigue level?

Touchpoints to look for worsening.

Have you had any fever / chills / sweats?

Any change to your cough?

Any change to your shortness of breath?

Anyone in the home or family been ill?

IF + findings concerning for URI or worse –

Obtain as much information about start of illness.

If concerns for viral illness – ensure appropriate OTC symptom relief.

If concerns for bacterial illness – prescribe abx with/without steroid burst

If concerns about significant illness – call to obtain follow up visit with local pulmonary.

If concerns about acute worsening such as an AEx, may need to go to hospital for admit / testing.

Review phone call and follow up appt reminder

Today I will _____. Remember your follow up appointment is scheduled with Dr. _____ on _____ at _____.

Make sure everything is scheduled – should have PFTs and 6 MWT and labs q 3 months.

